### 7.3 Enzalutamide

The most common adverse reactions ( $\geq 10\%$ ) in patients treated with enzalutamide are asthenia/fatigue, back pain, decreased appetite, constipation, arthralgia, diarrhea, hot flush, upper respiratory infection, peripheral edema, dyspnea, musculoskeletal pain, weight decreased, headache, hypertension, and dizziness/vertigo.

#### 7.3.1 Hot flashes

Hot flashes are common with treatment with enzalutamide. If  $\geq$  grade 3 hot flashes occur, enzalutamide may be reduced to the next lower dose level, at the discretion of the treating physician. Pharmacologic intervention with low-dose SSRI (or an alternative oral therapy that has been demonstrated to have beneficial effect for treatment of hot flashes greater than that reported for placebo e.g. clonidine, bupropion) may be administered. If  $\geq$  grade 3 hot flashes persist at the lower dose level and pharmacologic intervention with the above treatments has been unsuccessful, a second dose reduction may be instituted. If  $\geq$  Grade 3 hot flashes persist at lowest treatment

dose (50mg), patient will be taken off study, and adverse effect will be reported as intolerable toxicity. If  $\leq$  grade 2 hot flashes persist at lowest treatment dose (50mg), patient may be taken off study at discretion of treating physician. This toxicity will be reported, but it will not constitute unacceptable toxicity for purposes of adverse event reporting.

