### 6.3.2 Enzalutamide

The daily dose of enzalutamide is 160 mg/day given in 4 capsules (40 mg each) by mouth. Enzalutamide capsules are administered once daily until disease progression or intolerable toxicity. The first ten subjects on the enzalutamide + taselisib arm at Vanderbilt will have blood draws for PKs as outlined in the study calendar.

Patients should be instructed to take the dose of enzalutamide at the same time in the morning (before noon) every day, with or without food. Enzalutamide should be taken with a glass of water. Patients should swallow the capsules as a whole and not chew, crush, or open them.

If the patient forgets to take her/his dose and it is past noon, then the dose should be withheld that day and enzalutamide should be restarted the following day. Missed or vomited doses will not be made up. The occurrence and frequency of any vomiting during a treatment cycle must be noted as an adverse event.

A sufficient number of enzalutamide capsules should be provided to the patient to last until the next visit or, at the investigator's discretion, to last until the next cycle. Patients will be instructed to bring their bottles of study drug and their medication diary with them to each study visit.

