## 7. EXPECTED TOXICITIES AND DOSING DELAYS/DOSE MODIFICATIONS

### 7.1 Dose Modifications/ Delays

Table 2 below lists dose level reductions for taselisib and enzalutamide. Please see section 7.2 to 7.4 for thresholds to reduce doses.

Table 2: Dose Modifications			
Taselisib dose level reductions			
Starting dose	First reduction	Second reduction	
4 mg daily	2 mg daily	Discontinue	
Enzalutamide dose level reductions			
Starting dose	First reduction	Second reduction	Third reduction
160 mg daily	120 mg daily	80 mg daily	Discontinue

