#### **8.2.1 Enzalutamide Formulation and Storage**

The drug is supplied as 40 mg capsules by Medivation and Astellas. The drug substance is formulated in the surfactant caprylocaproyl polyoxylglycerides, or Labrasol. The product will be supplied as white to off-white gelatin capsules containing 40 mg of enzalutamide.

Enzalutamide is to be handled and stored safely and properly in accordance with the study drug label.

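### Section 7.3.1 ties its hot-flash off-study rule to a 50 mg lowest enzalutamide dose that Table 2 does not list and 40 mg capsules cannot make

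*Combined protocol and SAP*

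**What the plan says.** Section 7.3.1 lets the treating physician lower enzalutamide by one level for grade 3 or worse hot flashes. If they continue despite drug treatment, "a second dose reduction may be instituted". Two rules then depend on what happens at the lowest dose:

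- Grade 3 or worse (mandatory removal): "dose (50mg), patient will be taken off study, and adverse effect will be reported as intolerable toxicity".
- Grade 2 or lower (discretionary removal): "grade 2 hot flashes persist at lowest treatment dose (50mg), patient may be taken off study at discretion of treating physician". The section adds that this case is reported but is not counted as unacceptable toxicity.

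Section 7.1 presents Table 2 as the list of dose levels for both drugs: "Table 2 below lists dose level reductions for taselisib and enzalutamide". It refers to Sections 7.2 to 7.4 for the thresholds at which to reduce. The row under "Enzalutamide dose level reductions" reads "160 mg daily 120 mg daily 80 mg daily Discontinue".

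On the product, Section 6.3.2 states: "The daily dose of enzalutamide is 160 mg/day given in 4 capsules (40 mg each) by mouth". It also tells patients to take the capsules whole, without opening them. Section 8.2.1 describes the supply as "gelatin capsules containing 40 mg of enzalutamide" and mentions no other strength.

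**The concern.** A rule that removes a patient from study needs a trigger that can occur. Here the trigger is toxicity at a named dose. That dose is missing from the table that defines the levels and cannot be made from the capsules described.

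Two things depend on it. One is when a patient with persistent hot flashes goes off study. The other is whether the event is reported as intolerable toxicity, or is recorded without counting as unacceptable. Section 7.3.1 calls hot flashes common with enzalutamide, so the section deals with an expected toxicity.

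Off-study status also touches other rules. Section 6.9 allows a patient with toxicity to one drug to stay on study on the other, at the physician's discretion. Section 6.6 bars a patient on the enzalutamide-only arm who stops enzalutamide for toxicity from crossing over to taselisib alone.

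**Working it through.** No sample-size formula applies. The check is whether each enzalutamide dose named in the document (a) appears in Table 2 and (b) is a whole number of 40 mg capsules.

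**Inputs**
- Starting dose 160 mg daily, as 4 capsules of 40 mg (Section 6.3.2).
- Dose levels 160, 120 and 80 mg daily, then discontinuation (Section 7.1, Table 2).
- Only strength described: 40 mg (Sections 6.3.2 and 8.2.1). Capsules are not opened (Section 6.3.2).
- Lowest dose in the hot-flash rule: 50 mg, stated twice (Section 7.3.1).
- Reductions described for hot flashes: two (Section 7.3.1).

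**Step 1: reproduce the plan's own figure.** 4 × 40 mg = 160 mg, which agrees with Section 6.3.2.

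**Step 2: capsules per dose = dose / 40.**

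| Dose | Capsules | Whole number? | In Table 2? |
|---|---|---|---|
| 160 mg | 160/40 = 4 | yes | yes, starting dose |
| 120 mg | 120/40 = 3 | yes | yes, first reduction |
| 80 mg | 80/40 = 2 | yes | yes, second reduction |
| 50 mg | 50/40 = 1.25 | no | no |

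**Step 3: follow the two reductions on Table 2.** The first goes from 160 to 120 mg and the second from 120 to 80 mg. The third entry is discontinuation. After the two reductions that Section 7.3.1 describes, the patient is at 80 mg. The gap to the figure in the rule is 80 − 50 = 30 mg.

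**Step 4: look for another source.** No other part of the document defines a 50 mg enzalutamide dose.

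A patient managed by Table 2 with the capsules described therefore never satisfies the dose condition in either hot-flash rule.

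**The case against.** The strongest reply is that the operative words are the reference to the lowest treatment dose, and that 50 mg is only a gloss in brackets. Section 7.3.1 describes two reductions, Table 2 has two non-zero reductions, and Section 7.1 presents Table 2 as the list of levels. A site could drop the bracket and use the last level in the table. That reading is available and is a fair limit on the point: the rule is not beyond use. But it means setting aside a number stated in both sentences, and Section 7.4 sends any change to the dose guidelines to the Protocol Chair in advance.

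A second reply is that other text covers the gap. Table 2 ends in discontinuation. Section 7.3.2 lists hot flush among the enzalutamide toxicities and takes a patient off study if a grade 3 or 4 toxicity has not resolved within two weeks. This stands in part, since some persistent grade 3 cases may be caught there. However, that rule sits under other toxicities, says nothing about grade 2 or lower, and does not repair the hot-flash trigger or its toxicity classification.

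A reader might also infer that early removal decides the clinical benefit rate, at 1/37 = 2.7 percentage points per patient. The documents do not support this as a general statement. Under Section 2.1 a complete or partial response counts without a 16-week condition, and under Section 6.9 some patients can stay on study on the other drug with scans continuing. The figure could apply only to a patient who is on the combination arm (Section 15.3 plans no formal analysis of the other arm), has stable disease as best response, is in the 4-week analysis set (Sections 15.5 and 15.7), and has gone through two reductions and failed drug treatment before week 16, in a trial that has reached its second stage. Nor do the documents show that sites will in fact act differently; that would be a prediction.

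**Conclusion.** The inconsistency is certain and internal to the document. Section 7.3.1 makes mandatory removal, discretionary removal and the reporting of intolerable toxicity depend on a dose that Table 2 does not contain and that whole 40 mg capsules cannot make (1.25 capsules). Read literally, the trigger cannot be reached.

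The reach is limited to off-study timing and toxicity classification for patients whose hot flashes persist after two reductions. Their number is not given. Sample size, type I error and the Simon boundaries are untouched, and no general effect on the clinical benefit rate follows.

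The conclusion assumes that Table 2 is the complete set of enzalutamide levels and that 40 mg is the only strength used, which is what Sections 7.1, 6.3.2 and 8.2.1 state. It takes no view on which dose is right.

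**What to change.** Reconcile Section 7.3.1 with Table 2 in Section 7.1 and with the capsule description in Sections 6.3.2 and 8.2.1, so that the lowest dose, the off-study trigger and the toxicity-reporting trigger all refer to one level. Correct both sentences in Section 7.3.1, because each carries the 50 mg figure.

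In the same edit, check that the result agrees with Section 6.9 (continuing on the other drug after toxicity) and Section 7.3.2 (the two-week limit for grade 3 or 4 toxicity), and state which rule governs hot flashes. Which level and which rule apply is for the sponsor to decide.

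The cost is a short text correction by protocol amendment, with no change to the design or the statistical analysis.

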### 7.3.2 Other toxicities

Asthenia/fatigue, back pain, diarrhea, arthralgia, hot flush, peripheral edema, musculoskeletal pain, headache, upper respiratory infection, muscular weakness, dizziness, insomnia, lower respiratory infection, spinal cord compression and cauda equina syndrome, hematuria, paresthesia, anxiety, and hypertension have all occurred on studies of enzalutamide.

Though not expected, if  $\geq$  grade 3 diarrhea occurs that is not controlled with anti-diarrheal agents (e.g. loperamide), enzalutamide should be withheld until resolution to  $\leq$  grade 1, then reinstated at the next lower dose level.

If toxicities are  $\leq$  grade 2, manage symptomatically if possible and retreat without dose reduction.

If toxicities are  $\geq$  grade 3, except for anemia, treatment should be withheld until resolution to  $\leq$  grade 1 or baseline if baseline was greater than grade 1, then reinstated, if medically appropriate, at the next lower dose level.

For any grade 3 or 4 toxicity not mentioned above, treatment should be withheld until the patient recovers completely or to grade 1 toxicity. The treatment should then be resumed at the next dose level. For grade 1 or 2 toxicities, no dose reduction should be made.

A maximum of two weeks will be permitted for resolution of grade 3 or 4 toxicities. If toxicity has not resolved by the end of two weeks, patient will be taken off study.

## 7.4 Special Considerations

- For toxicities which are considered by the treating investigator unlikely to develop into serious or life-threatening events (e.g. alopecia, altered taste etc.), treatment may be continued at the same dose without reduction or interruption.
- The treating investigator may reduce a subject's dose for a toxicity of any grade/duration where s/he believes it to be in the best interests of the subject.
- Any consideration to modification of the above dose modification guidelines should be discussed with the Protocol Chair for approval or disapproval in advance.
- Study participants should be given instructions to minimize sun exposure (i.e. use SPF  $\geq$  30 sunblock, wear hats and long-sleeve clothing) due to the possibility of photosensitivity.
- As referenced above, pneumonitis has rarely been reported in clinical trials with taselisib. All patients should be routinely asked about the occurrence of adverse events which could include new or changed pulmonary symptoms (consistent with lung abnormalities). CT scans and pulmonary function tests should be done, as clinically indicated, or if there are symptoms that indicate that the patient has developed pneumonitis. In case of a documented pneumonitis, the guidelines (including dose

modifications) in the table above should be followed. Consultation with a pulmonologist is highly recommended for any pneumonitis case during the study.

## **8. DRUG FORMULATION/STORAGE/SUPPLY**

### **8.1 Taselisib**

Taselisib is an investigational agent and will be supplied free-of-charge from Genentech.

#### **8.1.1 Taselisib Formulation and Storage**

Drug Product taselisib (GDC-0032) is intended for oral administration. The taselisib tablet is a white, film-coated, immediate-release formulation of 2 mg strength, consisting of taselisib API, lactose monohydrate, microcrystalline cellulose, croscarmellose sodium, magnesium stearate, and Opadry 2 white film coating.

Taselisib tablets should be stored at 59°F–86°F (15°C–30°C) and should be protected from light.

For additional details, see the taselisib Investigator's Brochure.

### **8.2 Enzalutamide**

Enzalutamide will be provided free of charge by the study.

#### **8.2.1 Enzalutamide Formulation and Storage**

The drug is supplied as 40 mg capsules by Medivation and Astellas. The drug substance is formulated in the surfactant caprylocaproyl polyoxylglycerides, or Labrasol. The product will be supplied as white to off-white gelatin capsules containing 40 mg of enzalutamide.

Enzalutamide is to be handled and stored safely and properly in accordance with the study drug label.

### **8.2 Drug Accountability**

Accountability for the drug at all study sites is the responsibility of the site Principal Investigator and designated Pharmacy representative. The investigator will ensure that the investigational drug is used only in accordance with this protocol. Drug accountability records indicating the drug's delivery date to the site, inventory at the site, use by each patient, and return to Genentech or Medivation will be maintained by the clinical site. Of note, only unopened medication packages (i.e. not dispensed to patients) will be returned to Genentech or Medivation if not used. Drugs returned by patients will be destroyed according to each institution's policy. Accountability records will include dates, quantities, lot numbers, expiration dates, and patient numbers.

## **9. CORRELATIVE/SPEIAL STUDIES**

## 9.1 Advanced imaging correlative (Vanderbilt only)

Patients enrolling at Vanderbilt will be screened for participation in an advanced imaging correlative study, to be conducted through collaboration with investigators at the Vanderbilt University Institute for Imaging Science (VUIIS). The advanced imaging correlative will consist of multiparametric magnetic resonance imaging (MRI) to be performed at the VUIIS facility at three timepoints, chosen to coincide with the timing of required core biopsies: baseline, at day 14-21 following treatment initiation, and at the end of treatment.

Multiparametric MRI examinations will be designed and made available for four body sites – breast/axilla, lower neck/supraclavicular region, liver, and pelvic bone marrow – and patients will be eligible to participate in the advanced imaging correlative if their required core biopsies are obtained from one of these four body sites. Participation will be mandatory for patients accruing at Vanderbilt who meet the criteria outlined below, including presence of measurable disease (defined as at least one lesion measuring at least 10 mm in long axis diameter) at the body site of interest. If participation in the MRI sub-study is not possible due to scheduling issues, MRI weight limits, eligibility, or safety concerns over implanted medical devices, subjects may still continue with the rest of the study.

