- l Tumor assessment should be performed approximately every 2 cycles (up to -5 days) while on study treatment and at End-of-treatment visit if not obtained within the past 6 weeks. Scans should consist of CT scan of the chest, abdomen, and pelvis and a bone scan at baseline. Subsequent scans should consist of CT chest, abdomen and pelvis, and bone scan if bone metastases were present on the baseline studies. At the end of treatment, all scans (baseline and through disease progression) should be sent on a CD to the Vanderbilt Cancer Imaging Support Laboratory for central review and assessment. See Section 10.5 for details and address.
- m Archived tumor biopsy specimen: 20 unstained slides of archived biopsy block (unstained slides) or fresh tumor biopsy will be requested at the time of enrollment prior to initiation of treatment.
- n Tumor biopsies will only be performed in the phase II portion. A tumor biopsy from a metastatic site will be obtained from patients prior to day 1, at cycle 2 day 14-21, and upon progression of disease. The third biopsy (at the end of treatment) will not be required for patients who are removed from study for reasons other than disease progression. A patient who undergoes a research biopsy procedure for the purpose of this protocol, and in whom inadequate tissue is obtained, is not obligated to undergo a repeat biopsy.
- o See section 9.1. Required only for patients at Vanderbilt and only in the phase II portion. This should be performed prior to tumor biopsy, if possible. If MRI sub-study is not feasible due to scheduling, MRI weight limits, etc., patients may still continue with the remainder of the study.
- p Subjects on the enzalutamide + taselisib arm should begin enzalutamide on day 1 of cycle 1, and taselisib on day 1 of cycle 2.
- q Pill Diary can be found in the packet of supplemental forms.
- r See Section 6.4.2.
- s Phase II only. Biopsy questionnaire should be filled out by the patient on C3D1. Form can be found in the packet of supplemental forms.
- t The cycle 2 day 8 visit is only needed for patients on the combination of taselisib + enzalutamide. Patients on enzalutamide only do not need a visit on this day.

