### 6.3.1 Taselisib

Taselisib tablets are administered once daily until disease progression or intolerable toxicity. Taselisib administration will begin on C2D1 for patients enrolled on the combination arm (with enzalutamide alone beginning on C1D1). Each dose should be taken with a minimum of 3–4 ounces (90–120 mL) of water with or without food in the morning (before noon). If a dose is missed (not taken by noon), the patient will resume dosing with the next scheduled dose. Missed or vomited doses will not be made up. The occurrence and frequency of any vomiting during a treatment cycle must be noted as an adverse event. Patients should swallow the capsules as a whole and not chew or crush them.

A sufficient number of taselisib tablets should be provided to the patient to last until the next cycle. Patients will be instructed to bring their bottles of study drug and their medication diary with them to each study visit.

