### 9.2.3 Fresh biopsy of metastatic site

Once a patient is confirmed to be AR positive, meets all other eligibility, and registers for the study, collection of tissue from a metastatic site, if reasonably safe, is also a requirement for entry to this study. A biopsy can also be used for AR testing for the study (see Section 5). Pre-trial and day 14-21 biopsies should be collected. Research tissue blocks prepared from

these metastatic biopsies will not be returned. **All patients must have a biopsy of a metastatic site at the end of treatment if the patient is removed for disease progression or is on the enzalutamide only arm and crossing over to enzalutamide + taselisib. See section 9.2.4 below for details on collecting tissue.**

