#### **9.7 Biopsy Questionnaire**

A questionnaire will be given to each participant to complete at cycle 2, day 1. This questionnaire is designed to assess the impact of the multiple biopsies on the patient's quality of life and overall experience with the study.

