## 15.6 Analysis of Secondary Endpoints

We will calculate the ORR and corresponding 95% confidence intervals at the dose recommended for phase II. The overall PFS data for the patients at the dose recommended for phase II will be estimated using the Kaplan-Meier method with 95% confidence intervals.

Biopsy analysis will be performed in conjunction with the Pathology and Tissue Informatics Core to assess baseline, therapy-induced changes and status upon progression of the following: proliferation (Ki67), mitosis (mitotic index), apoptosis (cleaved caspase 3 levels by IHC), genomic instability (H2AX by IHC), levels of PTEN by IHC, PI3KCA mutational analysis, HER2 (IHC, FISH) and ER/PR levels (IHC). Levels of MEK [total and phosphorylated ERK1/2 (pERK1/2)] and AKT [phosphorylated AKT, S473 (pAKT)] will be measured by IHC.

RNA-seq will be performed on all biopsies to assign a triple negative subtype, to determine baseline and treatment-induced changes in GE after 5-10 days of therapy and define mutations present in the tumors both at baseline and upon progression of the disease. We expect an enrichment of drug resistance-associated mutations/gene amplifications particularly in tumors that regress and later recur while on therapy. Somatic SNPs and structural variants will be validated by whole exome sequencing (WES) of genomic DNA from the tumor and matched blood. We will validate mutations by targeted capture approaches that allow high-level coverage (greater than 200X) and analysis of clonality. The status of p53, BRCA1/2, PIK3CA, PTEN, INPP4B and other mutations associated with TNBC in the tumor tissue is critical for testing our hypothesis. This genetic information is key for determining the prognostic significance of mutations relative to response of agents being tested and for understanding mutation selection relative to the underlying genetic milieu of each tumor at time of entry into the trial. We anticipate significant opportunity for discovery of novel mutations as well as those arising from selection during resistance to the therapies under investigation. Statistics on the correlative endpoints (tissue assays and MRI scan) will be primarily descriptive. Therefore, these studies are considered to be exploratory and potentially hypothesis-generating.

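### After the lead-in amendment, Section 9.1 and the study calendar time the on-treatment MRI and biopsy 28 days apart, one before taselisib starts and one during it

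*Combined protocol and SAP*

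**What the plan says.** **Drug start.** Section 6.3.1: "Taselisib administration will begin on C2D1 for patients enrolled on the combination arm", with enzalutamide alone from C1D1. Calendar footnote p agrees, and Section 7.2.1.3 explains the 28-day lead-in as a response to early rash on the combination arm.

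**On-treatment MRI and biopsy.**
- Section 9.1 sets the MRI timepoints at "baseline, at day 14-21 following treatment initiation, and at the end of treatment" and says they were "chosen to coincide with the timing of required core biopsies".
- Section 9.2.3 says "Pre-trial and day 14-21 biopsies should be collected". Sections 1 and 9.1.3 give the same days. None of the three names a cycle.
- Calendar footnote n puts the biopsy "at cycle 2 day 14-21, and upon progression of disease". The calendar's biopsy and MRI rows both carry day 14-21 under the cycle 2, day 15 column.
- Footnote o, for the MRI, gives no time and refers the reader to Section 9.1.

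**Related timings.**
- Section 15.6 plans to study "treatment-induced changes in GE after 5-10 days of therapy".
- Section 9.7: "A questionnaire will be given to each participant to complete at cycle 2, day 1". Footnote s: "Biopsy questionnaire should be filled out by the patient on C3D1".
- Section 9.5 has the first ten combination patients at Vanderbilt start taselisib on day 1 and enzalutamide on day 9.

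**The concern.** The lead-in moved the first taselisib dose by a full cycle. The calendar was updated for this, but Section 9.1 was not. A site that reads Section 9.1 literally would scan, and take the matched biopsy from, a combination patient who has not yet had any taselisib. A site that reads the calendar would do so after two to three weeks on it.

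The imaging hypotheses in Section 9.1.1 rest on change from baseline to this timepoint and on correlation with p-ERK1/2, p-S6 and p-AKT in serial biopsies. Section 15.6 plans to describe therapy-induced change in tissue. If the timepoint means different drug exposure at different sites, change on enzalutamide alone is pooled with change on the combination. The sample also costs the patient an invasive research procedure.

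**Working it through.** The plan gives no figure for this point, so the check is calendar arithmetic and a comparison of passages.

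**Inputs.** Cycle length 28 days (Phase II schema). Taselisib from C2D1 (Section 6.3.1). Visit window 3 days (calendar footnote a). Day of treatment start = day 1.

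**Formula.** Study day of cycle k, day d = 28 × (k − 1) + d.

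| Event | Calculation | Study day |
|---|---|---|
| First taselisib dose, C2D1 | 28 × 1 + 1 | 29 |
| Section 9.1, read literally | days 14 to 21 from C1D1 | 14-21 |
| Footnote n, cycle 2 day 14-21 | 28 + 14 to 28 + 21 | 42-49 |
| Questionnaire, Section 9.7 (C2D1) | 28 + 1 | 29 |
| Questionnaire, footnote s (C3D1) | 56 + 1 | 57 |

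**Taselisib exposure at the sample.**
- Section 9.1: 29 − 21 = 8 and 29 − 14 = 15, so 8 to 15 days before the first dose. With both visit windows at their extremes, the latest sample is day 21 + 3 = 24 and the earliest taselisib is day 29 − 3 = 26, so there is still no overlap. Counting the start as day 0 moves the window to study days 15-22, which also ends before day 29.
- Calendar: 42 − 29 + 1 = 14 and 49 − 29 + 1 = 21, so the 14th to 21st day on taselisib.
- The two readings are 42 − 14 = 28 days apart.

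**Section 15.6.** The 5th to 10th day of therapy is study day 5-10 from C1D1, or day 33-38 from C2D1 (29 + 4 to 29 + 9). Neither overlaps days 14-21 or 42-49, so no biopsy is scheduled then under either reading.

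**Section 9.7.** A questionnaire about multiple biopsies on day 29 comes 13 to 20 days before a cycle 2 biopsy (42 − 29, 49 − 29). It follows the second biopsy only if that biopsy is in cycle 1. Footnote s (day 57) comes 8 to 15 days after the cycle 2 biopsy.

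**Section 9.5.** Under its start order, a patient at day 14-21 would have had taselisib for 14 to 21 days and enzalutamide for 6 to 13 days (14 − 9 + 1, 21 − 9 + 1). This contradicts Section 6.3.1 and footnote p. Its first phase II PK sample (C1D8) also differs from footnote k (C2D1).

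**Effect of mixing.** Suppose taselisib shifts the mean change in a marker by δ, and a share p of post-amendment combination samples is taken in cycle 1. The pooled mean then carries (1 − p)δ of that shift: all of it at p = 0, none at p = 1. The documents give no basis for p.

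**Number affected.** The combination arm is planned at 37. Section 7.2.1.3 reports on 8 phase II combination patients treated before the lead-in; if all 8 count towards the 37, at most 37 − 8 = 29 remain. The figure falls further because phase Ib patients at the recommended dose count as evaluable for phase II (Section 15.4) but have no study biopsies (footnote n). Patients without an accessible lesion may also enrol on archived tissue (Section 4.1.11).

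**The case against.** The strongest reply is that the calendar already settles the timing. Section 6.5 sends sites to it for treatment-period assessments, footnote n names cycle 2, and the MRI row agrees. Section 9.1 itself ties the MRI to the biopsies. Only Section 9.1 counts from treatment initiation; Sections 1, 9.1.3 and 9.2.3 are incomplete and can be read as shorthand for footnote n.

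Much of this stands. A reader might infer that the on-treatment samples cannot show any taselisib effect. The documents do not support that: under the calendar the sample is taken on taselisib, and end-of-treatment samples also follow taselisib. Nor does Section 9 consistently imply zero exposure, since Section 9.5 would put some Vanderbilt patients on both drugs by day 14-21.

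The reply does not remove the contradiction. Footnote o sends the MRI reader to Section 9.1, and Sections 5.2 and 5.3 send sites to Section 9 for biopsy details. Sections 9.5 and 9.7 still fit a schedule with cycle 1 sampling, so a site could reasonably follow it. No passage says which text prevails.

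It is also fair that objectives 2.3 d and e ask for p-ERK1/2, p-S6 and p-AKT at baseline and progression, not early on treatment. Section 15.6 calls the correlative work descriptive and exploratory. Specimens are labelled with date and time (Section 9.4), so mixed timings could be identified afterwards.

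**Conclusion.** This is an internal contradiction left by the lead-in amendment. It is not a design that rules out a taselisib signal. Read literally, Section 9.1 gives a combination patient an on-treatment MRI and matched biopsy 8 to 15 days before taselisib; the calendar gives them on the 14th to 21st day of taselisib. Sections 1, 9.1.3, 9.2.3 and footnote o do not settle which applies, and Sections 15.6 and 9.7 add timings that do not fit the calendar.

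The consequence depends on sites following different passages, which the documents neither show nor exclude. If they do, the early-change analyses in post-amendment combination patients are weakened. A reader might go further and call the paired data uninterpretable, or count all 37 combination patients as affected. Neither follows: collection dates are recorded, and pre-amendment and unbiopsied patients fall outside the problem. The number affected is unknown and below 37. The primary clinical benefit rate analysis is not affected.

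**What to change.** 1. State the cycle in Sections 1, 9.1, 9.1.3, 9.2.3 and footnote o so that they match footnote n and the calendar rows (cycle 2, day 14-21). In Section 9.1, remove the count from treatment initiation.
2. In Section 15.6, replace the 5-10 day interval with the scheduled biopsy time.
3. Align Section 9.7 with footnote s (C3D1), so that the questionnaire follows the second biopsy.
4. Add to Section 15.6 that each on-treatment sample and scan is classified by actual taselisib exposure at collection, from the collection date and dosing record. Results would then be described separately for enzalutamide-only and combination exposure. This also covers patients treated before the amendment.
5. Reconcile Section 9.5 with Section 6.3.1 and footnotes k and p on the order of drug start and the PK days. Which order applies is for the sponsor to decide.

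Items 1 to 3 are text edits through the normal amendment process and add no procedures, because the calendar already holds these times. Item 4 needs one derived variable from data already collected.
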